3 OBJECTIVES AND ENDPOINTS

Table 1. Study Objectives and Endpoints

OBJECTIVES	ENDPOINTS
NDURE FEASIBILITY STUDY	
Primary	
To assess the feasibility of NDURE among white and AA HNSCC patients.	NDURE Accrual Rate NDURE Completion Rate NDURE Session Completion Rate Questionnaire Completion Rate
Secondary	
To assess the acceptability of NDURE to white and AA HNSCC patients and HNSCC providers.	Patient Satisfaction with the Interpersonal Relationship with the Navigator Scale Score Patient Satisfaction with Logistical Aspects of Navigation Scale Score
To determine the feasibility of a single dedicated navigator to manage a caseload of patients for the NDURE intervention	Navigator Caseload Navigator Time Allocation (Direct) Navigator Time Allocation (Indirect)
To evaluate the feasibility of collecting pre- and post-NDURE intervention outcome measures in this patient population	Study questionnaire completion rate
RCT of NDURE VERSUS USUAL CARE	
Primary	
To evaluate the preliminary clinical impact of NDURE compared with UC on delays starting PORT among white and AA HNSCC patients.	PORT Delay Time-to-PORT (TTP) Initiation
Secondary	
To evaluate the preliminary clinical impact of NDURE compared with UC on racial disparities in delays starting PORT among white and AA HNSCC	PORT Delay TTP Initiation

Table 1. Study Objectives and Endpoints

OBJECTIVES	ENDPOINTS
patients.	
To assess the preliminary clinical impact of NDURE compared with UC on barriers to care	Barriers Resolution Rate Unresolved barriers
To determine the preliminary clinical impact of NDURE compared with UC on cancer care delivery processes	Pre-surgical Radiation Consultation Pre-RT Dental Extractions Surgery to Pathology Report \leq 7 d Surgery to PORT Referral \leq 10 d RT Referral to Consult \leq 10 d RT Consult to Initiation \leq 21 d
To evaluate the preliminary behavioral mechanism of action of NDURE	Care Transition Measure-15 (CTM-15) Score Change from Baseline in Interpersonal Support Evaluation List-12 Scale Score Change from Baseline in Perceived Susceptibility Scale Scores Change from Baseline in Illness Perception Questionnaire-Revised (IPQ-R) Consequences Sub-Scale Score Change in Baseline from Perceived Barriers Scale Change in Baseline from Communication & Attitudinal Self-Efficacy Scale (CASE)-Cancer Score

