6.1.2 ADMINISTRATION AND/OR DOSING

6.1.2.1 NDURE

NDURE will be delivered in one-on-one, face-to-face sessions between the navigator and the participant in a clinic- or hospital-based setting. The NDURE intervention consists of three navigation sessions (Study Visits 2-4), which are expected to take 30-60 minutes each. The NDURE sessions (Study Visits 2-4) will coincide with the presurgical consult, hospital discharge, and 1st postoperative clinic visit (see **Section 1.3, Schedule of Activities**). These time points were chosen to facilitate case identification and coordination across key care transitions. Contact beyond the three prescribed sessions will occur with a frequency and modality (e.g. text message, email, etc.) dictated by patient and navigator need. The NDURE intervention will be delivered in the following settings: the MUSC Head and Neck Tumor Center and MUSC hospital. A single dedicated navigator with no competing clinical or administrative responsibilities outside of this trial will deliver the NDURE intervention. Full dose of the NDURE intervention will consist of completing all three navigation sessions. Because the administration schedule and dose of usual care is highly variable, the NDURE intervention will not be dose-matched to usual care on intensity, duration, and/or frequency. Participants in the trial are permitted to interact with other participants after randomization, regardless of treatment allocation. Such encounters may occur in waiting rooms before or after clinic appointments given the single-site design of the trial.

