8 STUDY ASSESSMENTS AND PROCEDURES

8.1 ENDPOINT AND OTHER NON-SAFETY ASSESSMENT

Feasibility

NDURE Accrual Rate is defined as the proportion of eligible patients who enroll in NDURE

NDURE Completion Rate is defined as the proportion of enrolled patients who complete the baseline assessment, at least two NDURE intervention sessions, and the final follow-up assessment

Navigation Session Completion Rate is the proportion of NDURE navigation sessions completed by each individual

Navigator Caseload is the number of simultaneous cases (on-trial participants) being navigated by the NDURE navigator

Navigator Time Allocation (Direct) is the time (in minutes), that the NDURE navigator spends directly interacting with the patient to identify and address barriers to timely, equitable PORT

Navigator Time Allocation (Indirect) is the time (in minutes), that the navigator spends generating and enacting each Barrier Reduction Plan that is not directly interacting with the patient

Questionnaire Completion Rate is the proportion of pre- and post-treatment questionnaires completed by enrolled patients

Acceptability

Satisfaction with the Interpersonal Relationship with the Navigator Scale Score is defined as the total score of this 9-item measure of the satisfaction of the interpersonal relationship with the patient navigator. This reliable and validated measure^{30,31} has been widely used in prior studies of PN. The total score of the measure ranges from 9 (minimum) to 45 (maximum); higher scores represent a better outcome (greater satisfaction with the interpersonal relationship with the navigator).

Satisfaction with Logistical Aspects of Navigation Scale Score is defined as the total score of the 26-item measure of the satisfaction of the logistical aspects of PN. This reliable and validated measure³² has been widely used in prior studies of PN. The total score of the measure ranges from 0 (minimum) to 78 (maximum); higher scores represent a better outcome (greater satisfaction with the logistical aspects of navigation).

Clinical Outcomes

PORT Delay is defined as the initiation of PORT more than 6 weeks (42 calendar days) from the date of the definitive surgical resection. In situations in which the surgical management of the primary tumor and

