9 STATISTICAL CONSIDERATIONS

9.1 STATISTICAL HYPOTHESES

- Primary Endpoint:

PORT Delay

We hypothesize that, compared with patients who receive usual care, patients who receive NDURE will have a decreased rate of PORT delay (initiation of PORT > 6 weeks after surgery). Alternatively, our null hypothesis is that there will be no difference in the rate of PORT delay between NDURE and usual care.

The preliminary efficacy analysis will be calculated for the primary endpoint over the 6 week time period from the date of definitive surgical resection of the primary tumor.

- Secondary Endpoints:

PORT Delay

We hypothesize that, compared with usual care, NDURE will result in a smaller difference in the rate of PORT delay (initiation of PORT > 6 weeks after surgery) between AA and white patients. Alternatively, our null hypothesis is that there will be no difference in the rate of PORT delay between AA and white patients between NDURE and usual care.

The preliminary efficacy analysis will be calculated for the primary endpoint over the 6 week time period from the date of definitive surgical resection of the primary tumor.

TTP

We hypothesize that, compared with patients who receive usual care, patients who receive NDURE will have a shorter median TTP (time, in days, between the date of definitive surgical resection to the initiation of PORT). Alternatively, our null hypothesis is that there will be no difference in median TTP between NDURE and usual care.

TTP

We hypothesize that, compared with usual care, NDURE will result in a smaller difference in the median TTP between AA and white patients. Alternatively, our null hypothesis is that there will be no difference in the median TTP between AA and white patients between NDURE and usual care.

NDURE Accrual

We hypothesize that at least 60% of eligible subjects for the NDURE study will accrue to the study. Alternatively, our null hypothesis is that less than 60% of eligible subjects for the NDURE study will accrue to the study.

The preliminary feasibility analysis will be calculated for the secondary endpoint using the first 25 patients eligible to accrue to the study, which is expected to occur over 4 months.

NDURE Completion

We hypothesize that at least 85% of subjects who enroll in the NDURE study (at least 13 of 15 subjects) will complete all 3 NDURE sessions. Alternatively, our null hypothesis is that less than 13 of the 15 subjects who enroll in the NDURE study will complete all 3 NDURE sessions.

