9.2 SAMPLE SIZE DETERMINATION

9.2.1 NDURE FEASIBILITY STUDY

Power and sample size calculations were performed using the University of Iowa Binomial Distribution applet. The sample size justification for this single-arm study is based on the primary feasibility endpoints of NDURE accrual and completion. In the RCT of NDURE, we plan to enroll 60% of eligible patients. We expect similar accrual in this feasibility study. Therefore, we hypothesize that at least 60% of eligible subjects for the NDURE study will accrue to the study. Alternatively, our null hypothesis is that less than 60% of eligible subjects for the NDURE study will accrue to the study. Accruing to NDURE will be considered feasible if at least 15 of 25 eligible subjects enroll. Our sample size for the feasibility study was selected to provide a small probability of having an observed accrual rate of at least 60% when the true accrual probability is actually less than 60%. For example, if the true accrual probability for our proposed design is 45% (35%), the probability of enrolling 15 or more of 25 eligible subjects is only 10% (1%). Additionally, we hypothesize that at least 85% of subjects who enroll in the NDURE study will complete all 3 NDURE sessions. Alternatively, our null hypothesis is that less than 85% of subjects who enroll in the NDURE study will complete all 3 NDURE sessions. That is to say, NDURE will be considered feasible if at least 13 of the 15 subjects enrolled complete all three NDURE sessions. Accordingly, our sample size for the single-arm study was selected to provide a small probability of having an observed completion rate of at least 85% when the true completion probability of the intervention is actually less than 85%. For example, if the true completion probability for our proposed design is 70% (60%), the probability that 13 or more of the 15 enrolled patients complete all three NDURE sessions is 13% (3%). Therefore, the probability of falsely declaring NDURE feasible is reasonably controlled based on this sample size.

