9.4.3 ANALYSIS OF THE SECONDARY ENDPOINTS

9.4.3.1 NDURE FEASIBILITY STUDY

NDURE completion rate will be analyzed as 1) the percentage of enrolled patients who attend all three NDURE sessions and 2) the proportion of three NDURE sessions that are completed. For navigator caseload, we will consider the frequency of simultaneous cases navigated. Navigator time allocation for direct and indirect time, as well as patient-report measures of satisfaction with navigation will be summarized as described above for continuous data. Study questionnaire completion rate will be calculated as the proportion of pre- and post-intervention questionnaires (n=5 each) completed. Qualitative data will be analyzed using established team codebooks and focus on the content, format, delivery, and timing of NDURE. Qualitative analysis of semi-structured interviews with patients and providers following the pilot will be analyzed using established codebooks from the study team for evaluating the feasibility and acceptability of clinic-based HNSCC interventions with a focus on the content, format, delivery, and timing of NDURE.

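### Feasibility study: NDURE Completion Rate has two conflicting definitions, and the false-pass control claimed in Section 9.2.1 holds only well below the 60% and 85% targets

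*Combined protocol and SAP*

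**What the plan says.** **Definition.** Section 8.1 defines NDURE Completion Rate as the "proportion of enrolled patients who complete the baseline assessment, at least two NDURE intervention sessions, and the final follow-up assessment". Section 9.1 instead hypothesises that "at least 85% of subjects who enroll in the NDURE study (at least 13 of 15 subjects) will complete all 3 NDURE sessions". Section 9.2.1 sets the decision rule on the same basis: "NDURE will be considered feasible if at least 13 of the 15 subjects enrolled complete all three NDURE sessions". Section 9.4.3.1 analyses the completion rate in two ways, as "the percentage of enrolled patients who attend all three NDURE sessions" and as "the proportion of three NDURE sessions that are completed". Section 6.1.2.1 agrees with the three-session reading: "Full dose of the NDURE intervention will consist of completing all three navigation sessions". Section 8.1 also has a separate endpoint: "Navigation Session Completion Rate is the proportion of NDURE navigation sessions completed by each individual". The objectives table in Section 3 lists both under the primary feasibility objective: "NDURE Accrual Rate NDURE Completion Rate NDURE Session Completion Rate Questionnaire Completion Rate".

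**Error control.** Section 9.2.1 states the null hypotheses as true accrual below 60% and true completion below 85%. Accrual passes with at least 15 of 25 eligible patients, and completion with at least 13 of 15 enrolled patients. The section says the sample size makes a pass improbable when the true rate is below those values. It gives examples at 45% and 35% (accrual) and at 70% and 60% (completion), then concludes that false declarations of feasibility are adequately controlled.

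**The concern.** One endpoint name carries two definitions. The same 15 patients could therefore be reported with completion rates on opposite sides of the 85% target, with nothing in the plan to say which figure is meant. The Section 8.1 composite serves the primary feasibility objective, yet Section 9 never analyses it. The second quantity that Section 9.4.3.1 places under completion is the one Section 8.1 calls Navigation Session Completion Rate.

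The error-control statement covers the whole of each null hypothesis but is supported only at rates 15 to 25 percentage points below the boundary. Each cut-off sits at or just above its target, so the chance of passing cannot be small for true rates just under it. Section 5.5 relies on the result when it says the 60% accrual target will already have been tested in this study. A reader would take a pass as stronger evidence than 25 or 15 patients can give.

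**Working it through.** **1. The two definitions**

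| Patient | Section 8.1 | Sections 9.1, 9.2.1, 9.4.3.1 |
|---|---|---|
| Three sessions, both assessments | completer | completer |
| Two sessions, both assessments | completer | not |
| Three sessions, no final assessment | not | completer |

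The second and third rows show that neither definition contains the other. For illustration, suppose 12 patients attend three sessions, 3 attend two, and all assessments are complete. Section 9 gives 12/15 = 80% and Section 8.1 gives 15/15 = 100%.

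A simple model shows the range. Assume independent attendance with the same probability q at each session, and complete assessments. Then P(all three) = q³ and P(at least two) = q³ + 3q²(1 − q).

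| q | All three | At least two |
|---|---|---|
| 0.80 | 51.2% | 89.6% |
| 0.90 | 72.9% | 97.2% |
| 0.95 | 85.7% | 99.3% |

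The values of q are assumptions, not figures from the plan.

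**2. The plan's own error figures**

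The inputs are the Section 9.2.1 rules: n = 25, pass at r = 15; n = 15, pass at r = 13. The exact pass probability is

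P(X ≥ r) = Σ C(n,k) pᵏ (1 − p)ⁿ⁻ᵏ, summed over k = r to n.

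For completion at p = 0.70: 105(0.70¹³)(0.30²) + 15(0.70¹⁴)(0.30) + 0.70¹⁵ = 0.0916 + 0.0305 + 0.0047 = 0.1268.

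| Rule | True rate | Computed | Plan |
|---|---|---|---|
| ≥15/25 | 45% | 9.6% | 10% |
| ≥15/25 | 35% | 0.9% | 1% |
| ≥13/15 | 70% | 12.7% | 13% |
| ≥13/15 | 60% | 2.7% | 3% |

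All four of the plan's figures reproduce.

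**3. The same rules across the rest of each null hypothesis**

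| Accrual, true rate | P(≥15/25) | Completion, true rate | P(≥13/15) |
|---|---|---|---|
| 50% | 21.2% | 75% | 23.6% |
| 55% | 38.4% | 80% | 39.8% |
| 59% | 54.5% | 84% | 56.1% |
| limit at 60% | 58.6% | limit at 85% | 60.4% |

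For completion at p = 0.85: 105(0.85¹³)(0.15²) + 15(0.85¹⁴)(0.15) + 0.85¹⁵ = 0.2856 + 0.2312 + 0.0874 = 0.6042.

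The cause is where the cut-offs lie: 15/25 = 60% and 13/15 = 86.7%. Solving for the true rate, the pass probability reaches 20% at 49.6% (accrual) and 73.6% (completion), and 50% at 57.9% and 82.6%. All four rates are inside the stated nulls. Because the tail increases with p, it is at most 9.6% for accrual of 45% or less and at most 12.7% for completion of 70% or less.

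**4. What a bare pass shows**

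The exact (Clopper-Pearson) 95% intervals at the cut-offs are 39% to 79% for 15/25 and 60% to 98% for 13/15.

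**The case against.** **On the definitions.** Three sections agree on all three sessions and the decision rule attaches only to that reading, so Section 8.1 is the lone outlier. Figure 1 places baseline questionnaires before enrolment, and Section 6.4 makes all visits mandatory for a participant to remain active. Sections 4.2.3.2 and 5.5 expect close to 100% attendance, in which case the two rates would nearly coincide. Section 9.4.1 provides generic frequencies and percentages that could cover the composite. Sections 9.1 and 9.4.3.1 also treat completion as a secondary endpoint, although Sections 3 and 9.2.1 treat it as primary.

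These points limit the size of the problem but do not remove it. Near-complete attendance is an expectation that this study is meant to test. The generic line does not rescue the composite, because Section 9.4.3.1 says specifically how the named endpoint is analysed, and the composite is not among the options.

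**On error control.** Section 9.2.1 presents its figures as examples and gives the true rates they belong to, so nothing is hidden. A high pass probability just below a cut-off set at the target is inherent in such a rule. At true accrual of 50% or 55%, failing is still more likely than passing. Section 5.5 says that with a 6-month extension, 52% accrual among African American patients and 29% among white patients would reach 150 (before the inflation to 170 in Section 9.2.2).

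All of that is true, and it is why the point is minor. Offering examples does not narrow the general sentence or the conclusion, both of which cover every rate below the targets. The contingency also has limits: with 96 African American patients screened, 50% accrual gives 48, short of the 50 needed.

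**Conclusion.** Both parts hold. NDURE Completion Rate is defined inconsistently, and the Section 8.1 version has no specified analysis. The difference between the two rates depends on attendance: 20 percentage points in the illustrative 12-and-3 split, and little if attendance and assessment completion approach 100%.

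The error-control statement in Section 9.2.1 is wrong as written, although its four examples are right. Within the stated nulls the chance of a false pass rises to nearly 59% for accrual and just over 60% for completion. These figures assume only that patients behave independently with a common probability, which is the binomial model the plan itself uses.

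The consequence is limited. The 13-of-15 rule is unambiguous, no section makes these criteria a stopping rule for the RCT, and the RCT's primary endpoint, sample size and analysis are untouched.

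**What to change.** - **Section 8.1:** define NDURE Completion Rate as all three sessions, to match Sections 9.1, 9.2.1 and 9.4.3.1. Give the composite of at least two sessions plus both assessments its own name, and keep its ascertainment at Visit 5 as in the Schedule of Activities.
- **Section 9.4.3.1:** add a line saying the composite is summarised descriptively. Label the proportion of sessions completed as Navigation Session Completion Rate.
- **Section 9.2.1:** limit the error-control statement to true accrual of 45% or lower (false-pass probability at most 9.6%) and true completion of 70% or lower (at most 12.7%). State the probabilities nearer the targets: 21%, 38% and 59% at accrual of 50%, 55% and 60%; 24%, 40% and 60% at completion of 75%, 80% and 85%.
- **Reporting:** give both observed rates with exact 95% confidence intervals.

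The cost is wording and a few restated probabilities. No patients, data collection, cut-offs or RCT features change. The one drawback for the authors is a less favourable error-control statement.
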